## 10.0 CONCOMITANT MEDICATIONS

Patients will have their medication list reviewed and documented in CRF at study entry. On a weekly basis, medication lists will be reevaluated for modifications/changes in prescription. Patients will also be requested to fill out a medication diary regarding the medications taken over the prior week for management of bladder symptoms including urinary urgency, frequency, dysuria, bladder pain, or systemic symptoms such as myalgias, fevers, chills, nausea, vomiting.

Patients may continue to take all of their routine medications:

- Subjects may take doses of nonprescription strength NSAIDS, acetaminophen (paracetamol), ibuprofen or acetylsalicylic acid (aspirin) for non-chronic headache, muscle pain, trauma or prophylaxis as long the dosing regimens comply with the recommended dose in the product labeling.
- Subjects may receive antihistamine therapy for colds or allergies at non-prescription doses.
- Subjects may take vitamin supplements within a dose range not associated with toxicity.
- Other treatments and medications that may affect immune function, that have known or suspected anti-tumor activity, or that could interfere with the imaging assessment of disease progression are not allowed for subjects including any and all chemotherapeutics.

- The use of other investigational agents is not permitted.
- Active immunotherapy is not allowed for any subject.
- Any antibiotic therapy or antimicrobial therapy will be disclosed at the start of each visit. Patients may take antimicrobial therapy as indicated for active infection.

## 11.0 ADVERSE EVENTS

### 11.1 Adverse Event

According to ICH guidelines (Federal Register. 1997; 62(90):25691-25709) and 21 CFR 312.32, IND Safety Reports, and ICH E2A, Definitions and Standards for Expedited Reporting, an adverse event is defined as follows:

An adverse event is any untoward medical occurrence in a clinical investigation subject administered a medicinal product and which does not necessarily have a causal relationship with this treatment. An AE can therefore be any unfavorable and unintended sign (including an abnormal laboratory finding), symptom, or disease temporally associated with the use of a medicinal product, whether or not considered related to the medicinal product.

Abnormal laboratory values for laboratory parameters specified in the study should not be recorded as an adverse event unless an intervention is required (repeat testing to confirm the abnormality is not considered intervention), the laboratory abnormality results in a serious adverse event or the adverse event results in study termination or interruption/discontinuation of study treatment.

Medical conditions present at screening (i.e., before the study treatment is administered) are not adverse events and should not be recorded on adverse event pages of the CRFs. These medical conditions should be adequately documented on the subject chart. However, medical conditions present at baseline that worsen in intensity or frequency during the treatment or post-treatment periods should be reported and recorded as adverse events.

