### 3.2 Study Population

The University of Washington Medical Center (UWMC) Department of Urology Clinic administers BCG to high-risk NMIBC patients receiving either induction or maintenance therapy approximately 40-50 times monthly. We will recruit 45 BCG-adults from the UWMC Department of Urology who are scheduled to receive 6 weekly doses of intravesical BCG. Patients

will be indicated to receive BCG by their primary treating urologist following evaluation of histology from bladder biopsy and/or transurethral resection of bladder tumor tissue, as part of guideline-based standard of care.

Eligibility criteria includes 1) age 18 years or older, 2) English-speaking, 3) diagnosis of American Urological Association (AUA) high-risk NMIBC, including high grade (HG) pT1 (invading only the lamina propria of the bladder), recurrent HG pTa (superficial tumors), HG pTa >3cm in size or multifocal, any carcinoma in situ, any variant histology, any lymphovascular invasion, and HG prostatic urethral involvement(3), 4) have not received acupuncture in the previous 3 months, and 5) willing and able to participate in trial activities. A member of the research team will manually review weekly schedules of full-time uro-oncology faculty (n=6) and fellows (2) to identify patients who meet eligibility criteria as potential study subjects. Patients eligible to participate in the study will be approached by PI/Attending Physician/Advanced Practice Provider/ in the clinic following their post-operative visit during which pathology is discussed and they are counseled regarding BCG induction therapy. Study details will be provided to the patient and informed consent will be discussed at this time. If informed consent is granted, the patient will enter into this trial. Patients who provide consent will be randomized 2:1 to receive weekly acupuncture pre-BCG treatment plus standard of care symptom management (Arm A) or to the waitlist control arm (Arm B), standard of care symptom management plus four coupons for acupuncture after study completion.

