Symptom management. All patients will receive standard of care medications to treat symptoms (e.g. anticholinergics such as oxybutynin, tolterodine, darifenacin, solifenacin, trospium, fesoterodine; Beta-3 adrenergic agonists such as mirabegron, local analgesics such as phenazopyridine, narcotic medications such as oxycodone if necessary, nonnarcotic medications such as Tylenol and non-steroidal anti-inflammatory medications) as indicated.

Arm B: Waitlist control arm. To minimize differences in experience between the acupuncture intervention and waitlist control arms, patients in the waitlist control arm will be escorted to the same Consultation room where the acupuncture is performed and asked to lie in a comfortable position (similar to Arm A) prior to their intravesical therapy for an identical period of time before being moved to a treatment room for intravesical instillation of BCG, according to the standard protocol detailed above. At the conclusion of the trial participants in the waitlist control arm will receive coupons to receive 4 free acupuncture appointments. All patients will receive standard of care to treat symptoms (e.g. narcotic and nonnarcotic medications, local analgesics, anticholinergic medications) as indicated.

Follow-up data collection. On a weekly basis, prior to BCG instillation and adjunctive acupuncture therapy (if applicable), patients in both the intervention and waitlist control arms will be assessed using the following metrics:

Week 1	EORTC-QLQ-NMIBC-24 EORTC-QLQ-C30 Medication Journal Assessment of complementary, alternative, and integrative therapies Acupuncture expectancy and treatment preference
Week 2	EORTC-QLQ-NMIBC-24 EORTC-QLQ-C30 CTCAE v.50 assessment of Systemic Therapy Toxicity assessing symptoms over the prior week Medication Journal
Week 3	EORTC-QLQ-NMIBC-24 EORTC-QLQ-C30 CTCAE v.50 assessment of Systemic Therapy Toxicity assessing symptoms over the prior week Medication Journal
Week 4	EORTC-QLQ-NMIBC-24 EORTC-QLQ-C30 CTCAE v.50 assessment of Systemic Therapy Toxicity assessing symptoms over the prior week Medication Journal
Week 5	EORTC-QLQ-NMIBC-24 EORTC-QLQ-C30 CTCAE v.50 assessment of Systemic Therapy Toxicity assessing symptoms over the prior week Medication Journal
Week 6	EORTC-QLQ-NMIBC-244 EORTC-QLQ-C30 CTCAE v.50 assessment of Systemic Therapy Toxicity assessing symptoms over the prior week Medication Journal
Week 7	EORTC-QLQ-NMIBC-24

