#### **11.5 Grading Adverse Event Severity**

All AEs will be graded in severity according to the NCI Common Terminology Criteria for Adverse Events (CTCAE) Version 5.0. If a CTCAE criterion does not exist, the investigator should use the grade or adjectives: Grade 1 (mild), Grade 2 (moderate), Grade 3 (severe), Grade 4 (life-threatening), or Grade 5 (fatal) to describe the maximum intensity of the adverse event.

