**APPENDIX C: Acupoint Location Diagram**

## APPENDIX D: STUDY CALENDAR

## Study Calendar

	Screening	Baseline data	Week 1 BCG 1	Week 2 BCG 2	Week 3 BCG 3	Week 4 BCG 4	Week 5 BCG 5	Week 6 BCG 6	Week 7 Follow Up
Procedure	within X days	1 week prior to BCG #1 +/- X Days	Day 1	+/- 7 Days					
Physical Exam	X		X	X	X	X	X	X	X
Medical History Clinicopathologic		X							
Demographic Data		X							
Current Use of CAM/IM		X							
Informed Consent		X							
ECOG	X								X
EORTC-QLQ-NMIBC-24			X	X	X	X	X	X	X
EORTC-QLQ-C30			X	X	X	X	X	X	X
CTCAE v5				X	X	X	X	X	X
Assessment of CAM/IM Use		X	X	X	X	X	X	X	X
Medication Journal			X	X	X	X	X	X	X
AE to Study Intervention				X	X	X	X	X	X
Vital Signs	X		X	X	X	X	X	X	X
UA			X	X	X	X	X	X	
Study Intervention Therapy			X	X	X	X	X	X	
Foley Cath bladder emptied			X	X	X	X	X	X	
BCG			X	X	X	X	X	X	
Bladder Void Time recorded			X	X	X	X	X	X

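### No CTCAE grade is scheduled before the first BCG and acupuncture in either arm, so worsening of a pre-existing symptom cannot be derived on the scale used to grade adverse events

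*Combined protocol and SAP*

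**What the plan says.** Section 11.1 sets two rules for conditions that precede treatment. The first is an exclusion: "Medical conditions present at screening (i.e., before the study treatment is administered) are not adverse events and should not be recorded on adverse event pages". The second is an exception to it, for "medical conditions present at baseline that worsen in intensity or frequency during the treatment or post-treatment periods", which do have to be entered as adverse events. The pre-existing state itself goes into the clinical record: "These medical conditions should be adequately documented on the subject chart". No grade is asked for there.

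Section 11.5 fixes the severity scale: "All AEs will be graded in severity according to the NCI Common Terminology Criteria for Adverse Events (CTCAE) Version 5.0".

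In the schedule in 3.3, Week 1 has the two EORTC questionnaires followed by "Medication Journal Assessment of complementary, alternative, and integrative therapies Acupuncture expectancy and treatment preference". CTCAE first appears at Week 2, with recall over the preceding week. Patients are approached about the study "in the clinic following their post-operative visit during which pathology is discussed", that is, after bladder biopsy or tumour resection.

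The synopsis makes physician-reported CTCAE v5.0 events a primary endpoint and states that there is no blinding. Section 3.3.1 sets the objective of evaluating safety and tolerability against best supportive care. Section 14.2.1 item 5 plans a descriptive report of acupuncture-associated events in Arm A.

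**The concern.** Deciding whether a symptom has worsened takes two measurements on one scale, one of them before treatment. The plan schedules the later CTCAE grades but not the first.

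This matters more here than in many trials because of when patients enter. The introduction lists pelvic pain, dysuria, urgency, frequency and nocturia among the effects of BCG. A patient recently operated on through the urethra could have some of these before the first instillation. If a grade 1 or 2 term is then recorded at Week 2, the CTCAE data alone cannot show whether it is new, worse, unchanged or improving. The assessor has to decide, knowing the patient's arm.

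At stake is how far CTCAE grades can support a comparison of tolerability between arms, and what they can contribute to the design of the Phase III trial that this pilot is meant to inform.

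**Working it through.** No formula applies, and the plan states no figure to reproduce. The check sets the schedules beside the adverse event rules.

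| Source | CTCAE before first treatment | CTCAE after treatment starts |
|---|---|---|
| 3.3, list by week | none at Week 1 | Weeks 2 to 7 |
| 8.1, visit table | none at enrolment or Week 1 | Weeks 2 to 7 |
| Appendix D, CTCAE row | blank at Screening, Baseline and Week 1 | six marks, Weeks 2 to 7 |

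The three schedules agree: 0 pre-treatment and 6 later CTCAE assessments per patient. Section 3.3 also says that adverse events are recorded weekly with CTCAE v5. That sentence does not exclude Week 1, but no schedule places the assessment there.

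- **Timing.** Section 3.3 puts the weekly assessments before that week's BCG and acupuncture. A Week 1 assessment would therefore be a true baseline. The Week 2 assessment, with its one-week recall, covers the week that follows the first instillation and, in Arm A, the first acupuncture session.
- **Start of recording.** Section 11.7 starts adverse event recording at first exposure to acupuncture, so it supplies no earlier grade. For Arm B, which has no acupuncture during the study, it names no start point at all.
- **What else is collected before treatment.** NMIBC-24 and QLQ-C30 are listed at baseline in 3.3 and again at Week 1 (Appendix D marks only Week 1). Section 8.1 has a pain assessment of bladder, back and pelvis before the first instillation. Section 10.0 has a medication list at entry and a weekly diary of medication for bladder symptoms. Section 11.1 has the chart entry.
- **Whether these give a CTCAE grade.** NMIBC-24 is patient-reported on a different scale. The pain check covers pain but not urgency, frequency or dysuria. Medication use is indirect. The chart entry needs no grade. No section links any of them to CTCAE grading.

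A change in CTCAE grade from before treatment therefore cannot be derived from the scheduled data in either arm.

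**The case against.** The strongest reply is that the rule in 11.1 works without a baseline CTCAE grade. It asks about intensity or frequency, not about a change of grade. The clinician has the sources listed above, and 7.3 and 7.6 have staff check for acute cystitis complaints before each instillation, including the first. Section 11.4 requires an onset date, and 11.6 makes attribution take account of the patient's clinical state and other interventions. A symptom dating from surgery would have an onset before treatment and should stay off the adverse event pages. This stands: a reader might infer that the rule cannot be applied at all, and the documents do not support that. Nor does 11.1 confine adverse events to worsening. New events count as well, and the worsening condition concerns only what was already present.

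A second reply is that no planned analysis uses the missing grade. Section 14.2.1 item 5 covers acupuncture-associated events in Arm A, where bruising and soreness at needle sites are expected. Section 14.3 states that there is no testing for these reports. Urinary symptoms are compared on NMIBC-24, which has a pre-treatment value. This also largely stands, and it limits the consequence. It does not remove it, because 3.3.1 still sets an objective of safety relative to best supportive care.

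A reader might go further and infer that leftover surgical symptoms will be counted as toxicity, diluting an arm difference by a calculable amount. That is not supported either. The documents give no rate of pre-treatment symptoms, the inference needs staff to disregard 11.1, and 14.2.1 plans no such between-arm contrast.

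A reader might also fault the Appendix D row "AE to Study Intervention" for starting at Week 2. That start is logical, because before the first session there is no exposure to report.

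**Conclusion.** The point holds in a limited form. Worsening of a pre-existing symptom can be judged clinically, but it cannot be derived on the CTCAE scale, and the judgement is made unblinded. The shortfall is one missing assessment per patient in both arms.

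The effect on reported toxicity is unknown. It depends on how many patients have urinary symptoms at the first visit, which the documents do not say. That some will have them is an inference from entry after biopsy or resection, not a stated fact.

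The consequence is greatest for the between-arm safety reading in 3.3.1 and for planning the next trial. It is small for the Arm A report in 14.2.1. The change is still worth making, because it is cheap and a baseline grade that was never recorded cannot be recovered later.

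**What to change.** Add the CTCAE v5.0 assessment, in both arms, to the Week 1 entry of 3.3, 8.1 and Appendix D, marked as completed before the first acupuncture session and the first instillation. Keep the one-week recall used at later visits.

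Add one sentence to 14.2.1: CTCAE toxicity is summarised by arm as the worst on-study grade that exceeds the Week 1 grade for the same term. This remains descriptive and needs no test. Worsening within a grade will not show in it, so it supplements the clinical rule in 11.1 and does not replace it.

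The acupuncture side-effect form can stay as scheduled.

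The cost is one more use of an existing form at an existing visit: seven CTCAE assessments per patient instead of six, or 45 × 1 = 45 extra assessments at full enrolment. Each takes a few minutes. Beyond that there are three schedule edits and one line of analysis text.

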### 11.2 Serious Adverse Event

An adverse event should be classified as an SAE if it meets one of the following criteria:

Fatal	Adverse event results in death.
Life threatening:	The adverse events placed the subject at immediate risk of death. This classification did not apply to an adverse event that hypothetically might cause death if it were more severe.
Hospitalization:	It required or prolonged inpatient hospitalization. Hospitalizations for elective medical or surgical procedures or treatments planned before enrollment in the treatment plan or routine check-ups are not SAEs by this criterion. Admission to a palliative unit or hospice care facility is not considered to be a hospitalization.
Disabling/incapacitating	Resulted in a substantial and permanent disruption of the subject's ability to carry out normal life functions.
Congenital anomaly or birth defect:	An adverse outcome in a child or fetus of a subject exposed to the molecule or treatment plan regimen before conception or during pregnancy.
Medically significant:	The adverse event did not meet any of the above criteria, but could have jeopardized the subject and might have required medical or surgical intervention to prevent one of the outcomes listed above.

### 11.3 Unexpected Adverse Event

An unexpected adverse event is defined as an event that has a nature or severity, or frequency that is not consistent with the applicable investigator brochure, or the prior medical condition of the subject or other treatment given to the subject. "Unexpected," as used in this definition, refers to an adverse drug experience that has not been previously observed and

reported in preclinical or clinical studies rather than an experience that has not been anticipated based on the pharmacological properties of the study drug.

#### **11.4 Monitoring and Recording Adverse Events**

All AEs will be assessed by the investigator or qualified designee and recorded in the CRFs. The investigator should attempt to establish a diagnosis of the event on the basis of signs, symptoms and/or other clinical information. In such cases, the diagnosis should be documented as the adverse event and/or serious adverse event and not described as the individual signs or symptoms. The following information should be recorded:

- Description of the adverse event using concise medical terminology
- Description as to whether or not the adverse event is serious, noting all criteria that apply
- The start date (date of adverse event onset)
- The stop date (date of adverse event resolution)
- The severity (grade) of the adverse event
- A description of the potential relatedness of the adverse event to study drug, a study procedure, or other causality
- The action taken due to the adverse event
- The outcome of the adverse event

#### **11.5 Grading Adverse Event Severity**

All AEs will be graded in severity according to the NCI Common Terminology Criteria for Adverse Events (CTCAE) Version 5.0. If a CTCAE criterion does not exist, the investigator should use the grade or adjectives: Grade 1 (mild), Grade 2 (moderate), Grade 3 (severe), Grade 4 (life-threatening), or Grade 5 (fatal) to describe the maximum intensity of the adverse event.

#### **11.6 Attribution of an Adverse Event**

Association or relatedness to the study agent will be assessed by the investigator as follows:

- Definite: The event follows a reasonable temporal sequence from exposure to the investigational agent, has been previously described in association with the investigational agent, and cannot reasonably be attributed to other factors such as the subject's clinical state, other therapeutic interventions or concomitant medications; AND the event disappears or improves with withdrawal of the investigational agent and/or reappears on re-exposure (e.g., in the event of an infusion reaction).
- Probable: The event follows a reasonable temporal sequence from exposure to the investigational agent and has been previously been described in association with the investigational agent OR cannot reasonably be attributed to other factors such as the subject's clinical state, other therapeutic interventions or concomitant medications.
- Possible: The event follows a reasonable temporal sequence from exposure to the investigational agent, but could be attributable to other factors such as the subject's clinical state, other therapeutic interventions or concomitant medications.
- Unlikely: Toxicity is doubtfully related to the investigational agent(s). The event may be attributable to other factors such as the subject's clinical state, other therapeutic interventions or concomitant medications.
- Unrelated: The event is clearly related to other factors such as the subject's clinical state, other therapeutic interventions or concomitant medications.

For general AE assessment, an AE is considered related if it is assessed as definitely, probably, or possibly related; unrelated if it is assessed as unlikely related or unrelated.

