## 2.0 INTRODUCTION TO THE PROTOCOL

## 2.1 Introduction

In 2019, the American Cancer Society estimates that approximately 80,470 Americans will receive new diagnoses of bladder cancer, of which approximately 75% will be new diagnoses of nonmuscle-invasive bladder cancer (NMIBC). As per the American Urological Association (AUA) Guidelines, the cornerstone of management of high-risk, NMIBC is an induction course of 6 weekly instillations of intravesical Bacillus Calmette–Guerin (BCG) treatment following resection of the tumor. Unfortunately, nearly 70% of patients receiving BCG report severe adverse events and approximately 40% of patients receiving induction BCG therapy necessitate treatment interruptions secondary to local or systemic adverse events including pelvic pain, dysuria, severe urgency, frequency, urge incontinence, nocturia, and/or infectious complications. These treatment-associated symptoms are problematic, resulting in decreased ability to adhere to the full course of treatment, which is associated with decreased clinical efficacy of BCG in reducing the risk of recurrence and progression of bladder cancer, as well as severely negatively impacting patients' quality of life. Consequently, there is a need for adjunctive therapies to minimize BCG-associated side effects in order to maximize the likelihood that patients will be able to adhere to the full course of therapy.

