Acupoints. Standard techniques for point location(19) will be utilized and Clean Needle Technique(20) will be followed. See Figure 2 for acupoint locations. The acupuncture points will be needled unilaterally at KI3, KI7, KI10, and SP6 on the lower leg. On the contralateral sided LI11 and LU7 will be needled on the upper extremity. The points BL31, BL32, and BL33 will be needled bilaterally near the sacrum. The points Yin Tang (EX-HN3) and DU20 will be needled on the midline and auricular Shen Men will be needled unilaterally on the same side as the upper limb points. There will be a total of 15 needle sites. Electro-stimulation will be administered to SP6 and KI7 at 1-10mA with a frequency of 20Hz. Needles will be retained for 30 minutes. Specific acupoint selection is based on previously published studies,(9, 10, 16) indications according to Traditional

Chinese Medicine (TCM) theory(19) and current understanding of innervation and neuromodulation of acupoints.(12)-(15) After the 30 minute-long treatment, the needles will be removed and the patient will be moved to the treatment room where BCG will be administered according to standard protocol.

Acupuncture needles. 32-40-gauge x 30mm-40mm Seirin acupuncture needles will be used on all acupoints. The needles and guide tubes are individually packaged and sterile. The manufacturer of Seirin acupuncture needles conforms to with GMP, AAMI (American National), ISO 9002, CE Mark (European Common Market), and WHO (World Health Organization) guidelines for quality and safety.(21)

Electroacupuncture. (EA) machines used will be FDA compliant medical devices.(22-24)

Licensing and credentialing of acupuncturists: Acupuncture treatments will be performed by Washington State licensed acupuncturists with National Certification Commission for Acupuncture and Oriental Medicine (NCCAOM) certification. Study acupuncturists will be credentialed by the Seattle Cancer Care Alliance (SCCA) and UWMC to provide acupuncture to oncology patients and will be supervised by the Lead SCCA Acupuncturist.

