### 14.2 Primary/Secondary Endpoints/Hypotheses and Analytical Methods

#### 14.2.1 Primary Endpoint

1. Trial recruitment (proportion enrolled versus eligible, reason for not enrolling) will be described via qualitative report.
2. Trial retention (proportion retained versus all enrolled, reason for not completing) will be described via qualitative report. Successful retention is defined as continued participation within the trial until 1 week following completion of induction BCG.
3. Protocol adherence (proportion adhered versus all enrolled, specifics for how protocol was not followed and why) will be described via qualitative report. Protocol adherence is defined as completion of the acupuncture interventions and follow-up surveys if randomized to the acupuncture arm or completion of the follow-up surveys if randomized to the control arm.
4. Clinic staff's responses to surveys assessing the healthcare burden of this protocol and time spent undergoing the acupuncture therapy for the experimental arm will be described via qualitative report.
5. Adverse events associated with acupuncture therapy in the experimental arm will be described via qualitative report.

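### Section 11.6 does not separate acupuncture from BCG when attributing adverse events, so the Arm A count of acupuncture-related events depends partly on the assessor

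*Combined protocol and SAP*

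**What the plan says.** Safety of acupuncture is the second primary endpoint in the synopsis. Section 3.1.1 item 3 measures it as CTCAE v5.0 events specific to acupuncture. Section 3.3.1 states the aim as a comparison with best supportive care, but 14.2.1 item 5 gives the analysis as: "Adverse events associated with acupuncture therapy in the experimental arm will be described via qualitative report".

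Section 11.6 holds the attribution rule. It has five categories, scored against a 'study agent' or 'investigational agent'. 'Possible' is defined as: "The event follows a reasonable temporal sequence from exposure to the investigational agent, but could be attributable to other factors". The next two are "Unlikely: Toxicity is doubtfully related to the investigational agent(s). The event may be attributable to other factors" and "Unrelated: The event is clearly related to other factors". The dividing line is then drawn: "For general AE assessment, an AE is considered related if it is assessed as definitely, probably, or possibly related". 'Unlikely' and 'Unrelated' count as unrelated.

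On timing, 3.3 says that after the 30-minute treatment "the needles will be removed and the patient will be moved to the treatment room where BCG will be administered". The weekly CTCAE assessment in 3.3 asks about the prior week. On background, 2.1 states that "nearly 70% of patients receiving BCG report severe adverse events" and that about 40% of induction patients need treatment interruptions because of adverse events. The synopsis states that there is no blinding.

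**The concern.** The primary safety endpoint rests on deciding which events belong to acupuncture, and two features of the plan make that decision uncertain.

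First, the agent being scored is not identified. The synopsis lists the investigational drug as not applicable, and the heading of 5.2.6 uses 'investigational agent' above text about BCG. An assessor reading 11.6 alone cannot be sure which treatment is meant.

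Second, if acupuncture is meant, 'Possible' requires only plausible timing and still applies when another therapy could explain the event. Arm A patients receive that other therapy, with a high toxicity rate, within the same visit. Dysuria or fever in the following days fits 'Possible', and it also fits 'Unlikely'. No written rule chooses between them, and the choice moves the event across the related/unrelated line.

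At stake is whether the safety report describes acupuncture or describes how assessors coded BCG effects. The control arm is the natural check on BCG background, but 14.2.1 plans no adverse event table by arm.

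**Working it through.** The plan states no expected rate of acupuncture-related events, no threshold and no safety power, so there is no figure to reproduce. The check has two parts.

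**Part 1: how far coding alone can move the Arm A count.**

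Inputs:
- Arm sizes: 45 patients at 2:1 (14.3), so 45 × 2/3 = 30 in Arm A and 15 in Arm B.
- *b*, share of patients with a BCG event: 0.70 (severe events, 2.1); 0.40 (interruptions for adverse events, 2.1, used as a stand-in); 0.20 (assumed low case).
- *s*, share of those patients whose BCG event is coded 'Possible' for acupuncture: assumed, 0 to 1.
- *a*, true rate of acupuncture events: assumed, 0 to 0.10, independent of BCG events.

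Formula: expected Arm A patients labelled related = 30 × [1 − (1 − a)(1 − b·s)].

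With no true acupuncture events (a = 0), this reduces to 30·b·s:

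| b | s = 0 | s = 0.25 | s = 0.5 | s = 1 |
|---|---|---|---|---|
| 0.70 | 0 | 5.3 | 10.5 | 21 |
| 0.40 | 0 | 3 | 6 | 12 |
| 0.20 | 0 | 1.5 | 3 | 6 |

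With a = 0.10 and b = 0.70, the count at s = 1 is 30 × [1 − 0.90 × 0.30] = 21.9, against 21.0 with no acupuncture events. At s = 0 it is 30 × 0.10 = 3.0, against 0. A real 10% rate is therefore almost invisible at one extreme of coding and plain at the other.

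**Part 2: whether other provisions settle the attribution.**

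- *CRF causality field (11.4).* Relatedness is described with respect to a study drug, a study procedure or another cause. BCG causation can be written there, but BCG is not named and it has no graded field of its own.
- *Acupuncture symptom form (3.3, and a separate row in Appendix D).* Arm A completes it weekly before the next session, so its window also contains a BCG instillation. Its content is not in the documents.
- *Type of event.* Section 2.6 lists mainly local needle effects, but also pain, bleeding and infection. Section 2.1 lists pelvic pain and infectious complications for BCG. Points BL31 to BL33 are needled near the sacrum (3.3), while the BCG visit assesses bladder, back and pelvic pain (8.1). Most needle-site events can be told apart from BCG effects; some pain and infection events cannot.
- *Control arm.* Section 3.3 schedules weekly CTCAE assessment in both arms. Section 11.7 starts adverse event recording at first exposure to acupuncture, which Arm B does not have during the study. These two must be reconciled before Arm B data can be relied on.

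**Precision of a by-arm comparison.** The 95% half-width for a difference in proportions at a common rate b is 1.96 × √[b(1 − b)(1/15 + 1/30)]:
- b = 0.70: 1.96 × √(0.21 × 0.10) = 0.28
- b = 0.40: 1.96 × √(0.24 × 0.10) = 0.30
- b = 0.20: 1.96 × √(0.16 × 0.10) = 0.25

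**The case against.** The strongest reply is that 11.6 already lets a sensible investigator reach the right answer. 'Unrelated' covers events clearly due to other interventions, and BCG cystitis is a well-described example. The related/unrelated split is for general assessment, and 14.2.1 item 5 does not cite it; 3.3.1 item 5 says acupuncture events are tracked on a dedicated form. The endpoint is descriptive, with no test (14.3) and no trial stopping rule (4.1). Expected acupuncture effects are mostly local.

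Much of this stands, and it rules out several stronger readings:
- A reader might infer that the rule forces BCG toxicity into the related column. It permits that coding; it does not compel it.
- A reader might infer that the safety endpoint cannot be interpreted at all. Needle-site events, the separate form and weekly CTCAE assessment in a BCG-only arm all argue against that.
- A reader might infer that BCG causation is not recorded anywhere. The 11.4 field allows it, though not as a separate graded item.
- A reader might infer that the Section 9 discontinuation criterion on toxicity attributable to acupuncture adopts the 'Possible' threshold. Section 9 does not say so, and it lists severe BCG toxicity separately.
- BCG does not follow every session without exception: 3.3 and 7.4 allow deferral, and the text does not say whether acupuncture is then still given.
- Arm B having no acupuncture-related events is normal for an add-on design and is not a fault.

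The reply does not supply a rule that separates 'Possible' from 'Unlikely' for an event with two candidate causes, an identified agent, or an analysis that uses the control arm.

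**Conclusion.** The point holds as a gap in attribution and reporting. Section 11.6 leaves the agent unnamed and the boundary between related and unrelated undefined for events that either treatment could explain, and 14.2.1 does not use Arm B to show the BCG background. The Arm A count therefore depends partly on the assessor.

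The bounds are 0 to about 21 of 30 patients at the 70% background figure, 0 to 12 at 40%, and 0 to 6 at an assumed 20%. They require every BCG event to be coded one way or the other; with half coded 'Possible' the figures are 10.5, 6 and 3. They are not forecasts. The 70% and 40% rates are the protocol's background figures rather than trial data, and the coding share and true acupuncture rate are assumptions.

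This is a cheap improvement to a descriptive pilot. It does not show that the safety endpoint is invalid. It is best made before data collection, because attribution not recorded at the time is hard to rebuild.

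**What to change.** 1. In 11.6, name acupuncture as the agent being scored, and add a second, separate attribution to BCG for every adverse event in both arms.
2. In 14.2.1, tabulate all adverse events by term, grade and arm regardless of attribution. Show events possibly related to acupuncture in their own row, beside the Arm B frequency of the same term.
3. If a list of expected acupuncture events is used, keep the insertion-site qualifier from 2.6 for pain, bleeding and similar local events. Do not count bladder or urinary events automatically: without the qualifier, bladder pain, haematuria and urinary infection would enter as acupuncture events whatever the assessor thought.
4. Reconcile 11.7 with the weekly CTCAE schedule in 3.3, so that Arm B adverse events are recorded from the first BCG visit.

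The cost is one extra CRF column, one descriptive table and some wording. The table will be imprecise, with a 95% half-width for the arm difference of about 0.25 to 0.30, so it should be presented as description and not as evidence that the arms are equally safe.
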